13.4.2 Primary Analysis of Primary Endpoint(s)

The primary endpoint is the percentage of infants in the PEDI sample within each trial arm whose pediatric clinician adhered to the guidelines regarding peanut introduction. The primary

endpoint concerns peanut introduction recommendation by the treating pediatric clinician only and not additional behavior by the treating allergist or by caregivers.

The primary endpoint will be computed using EHR data from the 4-month and 6-month WCCs as follows:

For low-risk infants:

- Adherence is achieved if the pediatric clinician recommends introduction of peanut products.
- Non-adherence is achieved if the pediatric clinician fails to recommend introduction.

For high-risk infants, adherence is assessed through three routes. A pediatric clinician is adherent if:

- The pediatric clinician does not order an sIgE test and refers the infant to an allergist.
- The pediatric clinician does order an sIgE test, the result is ≤ 0.35 , and the pediatric clinician recommends introduction.
- The pediatric clinician does order an sIgE test, the result is > 0.35 , and the pediatric clinician refers the infant to an allergist.

A pediatric clinician is non-adherent if:

- The pediatric clinician does not order an sIgE test and does not refer the infant to an allergist.
- The pediatric clinician does order an sIgE test, the result is ≤ 0.35 , and the pediatric clinician fails to recommend introduction.
- The pediatric clinician does order an sIgE test, the result is > 0.35 , and the pediatric clinician does not refer the infant to an allergist.

13.4.3 Supportive Analyses of the Primary Endpoint(s)

Consistent with the intent-to-treat principle, infants seen by all clinicians in each participating practice are included in the primary analysis (PEDI sample). Recognizing that some clinicians in treatment arm practices might decline to participate in the pre-study training and/or decline to utilize the CDS tool, we will also perform sensitivity analyses to investigate any change in these results that would be associated with excluding infants seen by each of these categories of non-participating clinicians: (1) declines training/uses CDS, (2) has training/declines CDS, (3) declines training and declines CDS.

The primary analysis will be repeated in the PEDI sample to evaluate the impact of missing data, clinician-level clustering, and type of pediatric clinician. Sensitivity analyses will be performed where 1) missing adherence data are not imputed and are left missing and 2) where missing data are imputed as being adherent. It is not possible to have missing data in the context of low-risk infants but is possible for high-risk infants. For high risk infants, adherence can be incomplete and data missing, if peanut-specific IgE is ordered for an infant but never conducted. Sensitivity analysis with a clinician-level random effect will also be performed to evaluate the impact of clinician-level clustering. Finally, sensitivity analysis will be conducted to assess any potential differences between types of pediatric clinicians (pediatricians and advanced practice nurses).

The primary analysis will be repeated in the PEDI sample combining all infants from both the high- and low-risk groups. Risk group and the interaction of risk group and intervention group will be included as fixed effects predictors.

The primary analysis will be performed again using the SEDI infant sample and adjusting for relevant covariates from the pediatric clinician questionnaire and practice site enrollment data. All questions in these forms and questionnaires will be explored one at a time for possible inclusion as covariates. Infants will be excluded from these analyses if information was not collected for each particular question.

Exploratory analyses will be conducted using data collected from the practice characteristics and clinician surveys. Specifically, we will examine whether the primary analysis differs according to practice-level interest in peanut allergy or affiliation with an allergy practice. We will also examine the potential influence of additional clinician education received outside of the study (i.e. professional conferences, research results, other teaching conduits).

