8.2.2. EHR Data Extraction

Data collection will take place at both the practice network (e.g., Lurie Community Connect, Peoria area-OSF and Unity Point, Alliance Chicago) or practice level for inclusion in the EHR study database.

Each practice will have an information technology analyst responsible for facilitating data extraction at the practice level. Data from participating practices' EHRs will be extracted on a weekly basis through an automated process established by Lurie Children's Data Coordinating Center team (DCC) and sent to DCC via a secure file transfer protocol (SFTP). Practices will be provided a data dictionary and natural language processing code to identify the appropriate elements and visits/services to extract. DCC will develop Extract Transform Load (ETL) scripts on behalf of the practice network (with the appropriate approvals from the practices). The ETL

scripts will be run weekly so that each week the Lurie Children's DCC data manager will have a complete EHR-based data file for reporting compliance and participation metrics. The weekly file will also be used to identify new providers hired by the practices who may need training in the intervention.

The EHR study database will include data from each of the following types of health care encounters documented in the EHR:

1. 4-month WCC
2. 6-month WCC
3. 9-month WCC
4. 12-month WCC
5. 15-month WCC
6. 18-month WCC
7. 24-month WCC
8. Additional sick visits until 30 months of age
9. Allergy visits until 30 months of age
10. Emergency department visits until 30 months of age

Table 8.2 presents the data elements that will be collected in the EHR study database. Partial PHI including the full date of birth, patient zip code, and date of service will be included.

Table 8.2 EHR Data Elements

| EHR Activities | Data Collected |
|---|--|
| Infant characteristics | Gender, race, ethnicity, date of birth, height and weight over time, patient zip code at 4- month WCC, patient zip code at 6-month WCC, health insurance type at 4-month WCC, health insurance type at 6-month WCC |
| Problem list | Type of problem, date problem entered, date problem resolved |
| Medications list | Medications ordered, order date |
| Primary care visits (well or sick) | Date of service, peanut product introduction recommendation (NLP based), severe eczema (NLP based), eczema ICD-10 code, food allergy ICD-10 codes, date of allergy referral, CDS-specific fields (intervention arm only) |

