13.6 Statistical Hypotheses

Primary hypotheses: In each of the high-risk and low-risk strata, the primary endpoint analysis performs a test of superiority to assess whether the proportion of infants whose pediatric clinician is adherent to PPA Guidelines is different in the intervention arm compared to the control arm. A multiplicity adjustment will not be applied to the primary analysis because high and low-risk children represent independent risk strata where pediatric clinicians must take different steps to achieve adherence.

Null hypothesis: $P(\text{intervention group}) = P(\text{control group})$ where P denotes the proportion adherent.

Alternative hypothesis: $P(\text{intervention group}) \neq P(\text{control group})$

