13.7 Sample Size Considerations

Power has been computed for primary and exploratory binary adherence outcomes and secondary peanut allergy outcomes. In order to compute power, six quantities have been specified: the type 1 error rate, the number of practice sites, the number of patients expected per practice site, the within cluster correlation, the average proportion adherent (or peanut allergic) over all practice sites and intervention arms, and the difference in proportion adherent (or peanut allergic) between the intervention and control arms. Calculations assume a type 1 error of 0.05. In this study, investigators can control the number of practice sites invited to participate in the study but cannot control the number of infants assessed at each practice site. Since deployment of the intervention and data collection are through the EHR, inclusion of additional practice sites does not require significant additional budget. Therefore, the choice of number of practice sites is based primarily on the number expected to participate and not on budgetary or statistical power concerns. We estimate that at minimum 30 clinics will participate. Using a preliminary EHR data pull, we estimate being able to assess on average 17 high-risk and 333 low-risk per clinic in 18 months for a total sample size of approximately 500 high-risk and 10,000 low-risk infants.

Since investigators cannot control the number of infants assessed, power calculations describe the differences between intervention arms in study outcomes that are detectable with 80% power for our given study sample sizes, rather than the sample sizes needed to be able to detect given differences between intervention arms in study outcomes.

Statistical power for primary and exploratory adherence outcomes: We assume a within cluster correlation of 0.07 for the pediatric clinician adherence outcomes, estimated from a preliminary EHR data pull. Similar studies have assumed lower correlations in the range of 0.001-0.01^{39,40} however, so we expect this estimate to be conservative. To further be conservative, we assume the average proportion adherent over all practice sites and intervention to be 0.50. These and the previously described assumptions and sample sizes allow us to detect with >80% power an absolute difference in proportions of adherence of $\geq 18\%$ in high-risk infants and $\geq 14\%$ in low-risk infants.

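### The sensitivity analyses in 13.4.3 exclude decliners' infants from the intervention arm only, so those comparisons lose the protection of randomization

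*Combined protocol and SAP*

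**What the plan says.** Section 13.4.3 keeps the infants of all clinicians in the primary analysis, in line with intent to treat. It then notes that "some clinicians in treatment arm practices might decline to participate in the pre-study training and/or decline to utilize the CDS tool" and plans sensitivity analyses "excluding infants seen by each of these categories of non-participating clinicians: (1) declines training/uses CDS, (2) has training/declines CDS". The third category is clinicians who decline both.

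Other sections show who can fall into these categories:

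- Section 3.2: control practices receive no study procedures, no extra guideline education and no EHR change.
- Section 8.2.2, Table 8.2: the EHR extract contains "CDS-specific fields (intervention arm only").
- Section 13.4.1: completion of pre-study training is captured for intervention-arm clinicians.

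Section 13.6 states the primary hypothesis as a test of "whether the proportion of infants whose pediatric clinician is adherent to PPA Guidelines is different in the intervention arm compared to the control arm". The plan gives no threshold for declining the CDS and no matching exclusion in control practices. It gives no estimator designed for non-uptake.

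**The concern.** Declining training or the CDS is behaviour after randomization that can be seen in one arm only. Some control clinicians would have declined if offered iREACH, but they cannot be identified and stay in the comparison. If clinicians who engage with guideline training differ in adherence from those who do not, the trimmed intervention arm differs from the control arm even when iREACH does nothing.

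A link between engagement and adherence is plausible. Under section 6.1.1 the CDS includes the order set for sIgE testing or referral and an addition to the anticipatory-guidance template. Under section 3.3 adherence is read from laboratory and referral orders and from clinician notes.

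What is at stake is how the supportive results are read. Under a sensitivity label, a result that is similar or larger looks like confirmation of the primary finding, or like the effect when iREACH is used. It is neither.

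**Working it through.** **Inputs from the plan.** Section 13.7: "Calculations assume a type 1 error of 0.05"; "We estimate that at minimum 30 clinics will participate"; 17 high-risk and 333 low-risk infants per practice; within-cluster correlation 0.07; mean adherence 0.50; differences "detectable with 80% power for our given study sample sizes". Section 13.6: two-sided alternative. Section 13.3: 1:1 allocation, so 15 practices per arm. Section 3.2: about 200 clinicians, or about 7 per practice.

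**Inputs not in the plan (assumed).** Share declining *q*; adherence gap *g* between engaged and declining clinicians apart from iREACH; and, for the simulations, the clinician SD and the engagement-adherence correlation.

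**Step 1. Reproduce the plan's detectable differences.** Effective n per arm = 15m / [1 + (m − 1) × 0.07].

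- High-risk: 15 × 17 / 2.12 = 120.3; SE = √(2 × 0.25 / 120.3) = 0.0645; 2.80 × 0.0645 = 18.1 points (plan: 18).
- Low-risk: 15 × 333 / 24.24 = 206.1; SE = 0.0493; 2.80 × 0.0493 = 13.8 points (plan: 14).

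**Step 2. Bias under no iREACH effect.** Let a share *c* of intervention clinicians, all decliners, be removed. Engaged clinicians then make up (1 − q)/(1 − c) of the intervention arm and 1 − q of the control arm, so

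bias = g × (1 − q) × c / (1 − c).

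If all decliners are removed (c = q), this is q × g. Take q = 0.30 and g = 0.20:

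- All three categories together: 0.30 × 0.20 = 6.0 points.
- One category holding a third of the decliners (c = 0.10): 0.20 × 0.70 × 0.10 / 0.90 = 1.6 points.

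**Step 3. Rejection rate, normal approximation, same q and g.**

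- Low-risk, all three: effective n falls to 15 × 233.1 / 17.25 = 202.7 in the intervention arm; SE = 0.0495; 0.060 / 0.0495 = 1.21; rejection about 22.8% (simulated 21.1%).
- Low-risk, one category: effective n 15 × 299.7 / 21.91 = 205.2; SE = 0.0493; 0.0156 / 0.0493 = 0.32; rejection about 6%.
- High-risk, all three: about 14.4% (simulated 13.5%).

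With g = 0, simulated rejection after exclusion was 4.2% to 6.1%. With all infants kept it was 4.4% to 6.1% over the whole grid.

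**Step 4. Simulation with practice and clinician random effects, no iREACH effect.** Settings: 30 practices, 7 clinicians each, mean adherence 0.50, practice ICC about 0.07, 30% declining. The test is a two-sided t-test on practice proportions. Low-risk infants; where two all-three rates are shown they come from separate sets of runs:

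| Clinician SD (logit) | Correlation | Bias, all three dropped | Rejection, all three dropped | Rejection, one category (a third of decliners) |
|---|---|---|---|---|
| 0.8 | 0.5 | +4.2 points | 12%, 13% | 6-6.5% |
| 0.8 | 0.8 | +6.5 points | 22%, 25% | 6.5-7% |
| 1.2 | 0.5 | +5.4 points | 15%, 19% | 5-5.5% |
| 1.2 | 0.8 | +8.9 points | 36%, 40% | about 8% |

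A further set of runs at correlations 0.5 to 0.8 gave about 14-45% for all three and about 5-8% for one category, with a bias of 1 to 2 points in the latter. Across the sets the range is about 12-45% against 5-8%. For high-risk infants, dropping all three gave 8% to 24%; dropping one category at SD 0.8 gave 5-6%. At zero correlation rejection is 5%. At a correlation of −0.3 with all decliners dropped, the bias reverses to between −2.5 and −3.3 points.

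**The case against.** **The primary claim is not at stake.** This stands. The primary analysis is intent to treat, the null in section 13.6 belongs to it, and no success criterion is attached to the exclusion runs.

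**The large rejection rates belong to a different analysis.** This largely stands. The wording of 13.4.3 most naturally means one category at a time. A reader might infer that the plan compares fully engaged iREACH clinicians with all control clinicians at an error rate of 12-45%. That is so only if all three categories are dropped together, which the text does not state. With one category dropped, inflation is slight unless decliners concentrate in that category.

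**The direction is not known.** This stands. A reader might infer that these analyses must show a larger effect than the primary one. Nothing in the documents establishes that. Clinicians who already follow the guideline may skip training or alerts as unnecessary, and the bias would then run against iREACH.

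**The inputs are assumed, and pilot uptake looked high.** The first part stands. On the second, section 1.4 reports that over 90% of clinicians in the pilot iREACH clinic distributed handouts. That is indirect evidence from one practice, but it gives no support for 30% declining. At q = 0.10 and g = 0.10, simulated rejection is 5.4% (low-risk) and 5.0% (high-risk).

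**CDS use is not the outcome.** A reader might infer that dropping CDS decliners amounts to deleting non-adherent records. The documents do not go that far: exclusion is by clinician, adherence comes from orders and notes rather than CDS fields, and nothing says orders can be placed only through the order set.

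What survives is that every variant selects on post-randomization behaviour in one arm, under a label that invites reading it as a robustness check.

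**Conclusion.** The point holds as a flaw in the supportive analyses. The exclusions can be applied only to intervention-arm clinicians, so the comparisons left over are not protected by randomization. They are biased whenever engagement is related to adherence apart from iREACH. Favouring iREACH is the likelier direction, but not a certain one.

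With the assumed inputs, the size runs from negligible (zero correlation, or one small category dropped) to serious (all decliners pooled and a strong correlation). The simulations test practice means, not the planned mixed model, and the one-category figures assume an equal split of decliners. The documents do not support reading this as a defect in the primary result. They also do not support treating the upper rejection rates as the error rate of the analyses as written. The change is worth making because it is cheap and uses data already collected.

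**What to change.** In section 13.4.3, replace the three exclusion comparisons with a complier-average estimate that keeps every infant in the PEDI sample and uses randomized arm as the instrument:

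estimate = (adherence in intervention arm − adherence in control arm) / *u*,

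where *u* is the share of intervention-arm infants whose clinician took up iREACH. Uptake in control practices is zero by design. Define uptake in advance as any training or any CDS use, with a stated criterion for CDS use. Give a cluster bootstrap or delta-method interval with practice as the unit. The test of no effect then rests on the randomized comparison.

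Do not compute a version with uptake defined as both training and CDS use, because clinicians with one component received part of iREACH. For illustration, let 60% take both and 20% take one, each with a true effect of 12.5 points. The arm difference is 0.80 × 12.5 = 10 points. Dividing by 0.60 gives 16.7, an overstatement of 4.2 points; dividing by 0.80 returns 12.5.

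Report adherence by training/CDS category descriptively within the intervention arm, next to the prompt-use summary already planned in 13.4.6, and state that it is not a treatment comparison.

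The cost is SAP wording and modest analysis time. The interval widens by roughly 1/*u*: about 1.11 times at *u* = 0.90 and 1.43 times at *u* = 0.70. The estimate also assumes that iREACH has no effect on clinicians who decline it. That is doubtful where the alert still fires at their visits, and the SAP must say so.

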13.4.4 Analyses of Secondary and Other Endpoint(s)

Analysis of the secondary endpoint will be performed separately for high- and low-risk infants. Incidence of peanut allergy will be analyzed with generalized linear mixed models in the PEDI sample in the same manner as the primary pediatric clinician endpoint with infants as the unit of analysis.

Data for diagnosis of peanut allergy (yes/no) from the 4 month - 30 month EHR data collection time points will be combined into one binary variable describing whether (yes/no) diagnosis occurred at any time up through the 30-month time point. Data from caregivers FOABF surveys at 12 and/or 24 months will be used to determine the presence of a caregiver reported peanut allergy or physician diagnosed peanut allergy.

The peanut allergy endpoint will be determined by combining information from EHR and caregiver survey information as described in the MOP.

Exploratory analyses of the secondary peanut allergy endpoint will include the following. Analyses will be treated as exploratory and hypothesis- generating, so no formal correction for multiple testing will be applied.

- The primary analysis of the secondary endpoint will be repeated to evaluate the impact of missing data. Missing data will be classified in three ways as follows:
 - Missing data are not imputed via multiple imputation and are left missing.

- Missing data are imputed as non-peanut allergic.
- Missing data are imputed as peanut allergic.
- The primary analysis of the secondary endpoint will be repeated combining all infants from both the high- and low-risk groups. Risk group and the interaction of risk group and intervention group will be included as fixed effects predictors.
- The primary analysis of the secondary endpoint will be repeated in the PEDI sample including pediatric clinician adherence, allergist adherence (high-risk only), their interaction, and their interactions with intervention group as fixed effects predictors.
- The primary analysis of the secondary endpoint will be repeated in the EEDI2 sample including pediatric clinician adherence, allergist adherence (high-risk only), caregiver adherence, and all two- and three-way interactions with each other and intervention group, as fixed effects predictors.
- The primary analysis of the secondary endpoint will be repeated in the EEDI2 sample including the presence and extent (e.g., duration and amount) of peanut exposure as predictors.

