- d. *A BPA* triggered when the pediatric clinician views peanut sIgE results (for those patients for whom sIgE has been ordered. The BPA will provide the criteria for "positive" results (≥ 0.35 kU/L) and a recommendation to refer to an allergy specialist if results are positive.

Caregiver Handout on How to Introduce Peanut Containing Products: Handout adapted from the NIAID caregiver materials (English and Spanish versions). The handouts were simplified and tested with caregiver groups including low-literacy, underserved families. This handout can be used as part of pediatric clinician counseling and can go home with caregivers as a reminder.

C. Follow-up Prompts at 9- and 12-month WCC: *Smart Texts and Data Elements* that advise the pediatric clinician to ask caregivers and chart whether peanut products have been introduced into their infant's diet. If the caregiver reports that peanut products were introduced, the clinician will be directed to document whether introduction was tolerated. If caregiver reports that peanut products were not introduced, the clinician will be directed to ask the caregiver for reasons why they did not.

Note: For those practices that do not use an Epic-based EHR, Lurie Children's study team will facilitate and work with their informatics teams to implement an iteration of the CDS tool that is compatible with the practice EHR.

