13.2 Endpoints

Primary Endpoints:

- % of infants at *low risk for peanut allergy* whose pediatric clinician adhered to the guidelines for that infant.
- % of infants at *high risk for peanut allergy* whose pediatric clinician adhered to the guidelines for that infant.

Secondary Endpoint:

- % of infants at *low risk for peanut allergy* who developed peanut allergy by age 2.5.
- % of infants at *high risk for peanut allergy* who developed peanut allergy by age 2.5.

Exploratory Endpoint 1:

- % of infants at *high risk for peanut allergy* whose allergist adhered to the guidelines.

Exploratory Endpoint 2: Pediatric clinician and caregiver reported knowledge, attitudes, and barriers and facilitators to PPA Guideline adherence.

Exploratory Endpoint 3: Each of the following endpoints include infants that are fully adherent and those that are adherent despite conflict with the clinician recommendation as defined in Figure 6. The endpoints for high risk infants can only be determined for infants where clinician testing (e.g. IgE and/or skin prick tests) is available in order to determine guideline consistent caregiver behavior.

- % of infants at *low risk for peanut allergy* whose caregiver introduced peanut by 12 months of age.

- % of infants at *high risk for peanut allergy* whose caregiver introduces peanut products by 7 months of age and continues feedings with at least 6 g of peanut protein over ≥ 3 feedings per week as reported around the infant's 1st birthday in accordance with the peanut allergy prevention guidelines.% of infants at *high risk for peanut allergy* whose caregiver introduces peanut products but does not do so by 7 months of age or does not continue feedings with at least 6 g of peanut protein or over ≥ 3 feedings per week as reported around the infant's 1st birthday. 13.3 Measures to Minimize Bias

A minimum of 30 participating clinic sites will be randomized in a 1:1 ratio to the intervention arm (i.e., offering iREACH intervention) or standard care (i.e. without iREACH). Using a computerized random number generator, the randomization will be stratified by practice site size to achieve balanced allocation of participants into the intervention and standard care arms. This process will be performed by the Lurie DCC biostatistician, who is blinded to the intervention delivery and will not be aware of the identity of participating sites.

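### Peanut-allergy detection through the EHR is prompted in the intervention arm only, and no planned analysis separates detection from incidence

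*Combined protocol and SAP*

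**What the plan says.** Section 13.4.4 collapses the EHR data from 4 to 30 months into one binary variable: "whether (yes/no) diagnosis occurred at any time up through the 30-month time point". It then adds caregiver-reported or physician-diagnosed allergy from the 12- and 24-month surveys and leaves the rule for combining the sources to the Manual of Procedures (MOP). Section 3.4 grades the result by source (allergist, pediatric clinician, caregiver) and by four diagnostic categories, from confirmed to no peanut allergy.

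Section 6.1.1 makes charting part of the intervention. At the 9- and 12-month visits clinicians are prompted to ask whether peanut has been introduced, and if it has, "the clinician will be directed to document whether introduction was tolerated". The same section describes an order set for sIgE testing or allergist referral according to risk, and an advisory to refer when sIgE is positive. Sections 3.2 and 6.1.2 give control practices standard care without EHR changes. Among the items extracted, Table 8.2 in section 8.2.2 lists "CDS-specific fields (intervention arm only").

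Section 13.4.4 plans three treatments of missing allergy data (left missing, all non-allergic, all allergic) and a model with peanut exposure as a predictor in the caregiver-survey sample (EEDI2).

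**The concern.** A recorded diagnosis needs both disease and an occasion to find it. iREACH is meant to reduce the disease, but it also creates occasions to find it in one arm: prompted questions, prompted charting and, in high-risk infants, guided testing and referral. The better the intervention works on the primary endpoint, the more such occasions its infants have.

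An imbalance is plausible on the protocol's own evidence. In the pilot (section 1.4), adherence for low-risk infants was 75/143 (52.4%) with iREACH and 44/311 (14.1%) without. Section 1.1 expects few caregivers to introduce peanut early unprompted. Section 12.1 concedes that reactions may go unrecorded in the EHR and that the study cannot control this.

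At stake is the interpretation of the secondary endpoint. A null or adverse result could reflect better detection rather than failure to prevent allergy, and nothing planned would tell the two apart.

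**Working it through.** **1. Sources of a yes, by arm**

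| Source | Intervention | Control |
|---|---|---|
| Problem list, ICD-10 codes, test results, allergy and ED visits (8.2.2) | extracted | extracted |
| 9- and 12-month prompts to ask and chart tolerance (6.1.1) | yes | no |
| Guided sIgE testing or referral, high-risk (6.1.1) | yes | no |
| CDS-specific fields (8.2.2) | extracted | do not exist |
| Caregiver surveys at 12 and 24 months (4.1, 13.4.4) | consenting caregivers | consenting caregivers |

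The ordinary EHR fields are extracted alike, but what enters them can be influenced by prompts present in one arm only.

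**2. The plan's own power figures**

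Inputs from section 13.7: "Calculations assume a type 1 error of 0.05"; differences "detectable with 80% power for our given study sample sizes"; "We estimate that at minimum 30 clinics will participate"; about 500 high-risk and 10,000 low-risk infants; within-cluster correlation 0.02; intervention v control proportions 5.4% v 13.8% (high-risk) and 0.11% v 1.50% (low-risk). Practices are "randomized in a 1:1 ratio to the intervention arm" or to standard care. A two-sided test is assumed, because section 13.6 states the primary hypothesis as whether adherence "is different in the intervention arm compared to the control arm".

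Design effect = 1 + (m − 1) × 0.02; effective n per arm = (N/2)/design effect; power = Φ[(Δ − 1.96 × SE pooled)/SE unpooled].

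- High-risk: m = 500/30 = 16.7; design effect 1.313; effective n = 250/1.313 = 190; power 79.7%.
- Low-risk: m = 10,000/30 = 333; design effect 7.647; effective n = 5,000/7.647 = 654; power 80.4%.

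The listed pairs reproduce (about 77% and 78% with a t reference on 28 df). They take ascertainment to be equal and complete in both arms. A separate matter to reconcile: section 13.7 states differences of 8.2% and 0.98%, but its own pairs give 13.8 − 5.4 = 8.4 and 1.50 − 0.11 = 1.39 points.

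**3. Effect of unequal detection on the risk ratio**

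Observed RR = true RR × (detection, intervention ÷ detection, control), with no false positives. All detection values here and in step 4 are assumptions.

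- 90% v 80%: 0.80 × 90/80 = 0.90; 1.00 × 90/80 = 1.13.
- 90% v 70%: 0.80 × 90/70 = 1.03.
- Equal detection: 0.80 stays 0.80.
- Reversed, 80% v 90%: 0.80 × 80/90 = 0.71, which overstates the benefit.

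**4. Effect on power and on apparent harm, if detection is higher in the intervention arm**

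Observed incidence = true incidence × detection. Power is at the planned true effects. The last two columns take the control incidence as true in both arms.

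| Stratum | Detection, int./control | Power | Spurious excess in intervention arm | Chance of significant harm |
|---|---|---|---|---|
| High-risk | 100/100 | 79.7% | 0 | 2.5% (nominal) |
| High-risk | 95/85 | 64.1% | 1.38 points | 6.0% |
| High-risk | 95/75 | 47.8% | 2.76 points | 13.0% |
| High-risk | 90/60 | 26.9% | 4.14 points | 26.3% |
| Low-risk | 100/100 | 80.4% | 0 | 2.5% (nominal) |
| Low-risk | 95/85 | 72.5% | 0.15 points | 4.2% |
| Low-risk | 95/75 | 65.6% | 0.30 points | 7.0% |
| Low-risk | 90/60 | 53.8% | 0.45 points | 11.7% |

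Example (high-risk, 95/85): the planned effect is observed as 0.95 × 5.4 = 5.13% v 0.85 × 13.8 = 11.73%. With no true effect it is 0.95 × 13.8 = 13.11% v 11.73%, an excess of 1.38 points.

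**5. Do the planned analyses cover this?**

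Each missing-data treatment applies one rule to both arms, and section 13.4.4 does not define missing. An infant with visits on file but no exposure or test may not count as missing at all. The exposure model uses survey responders and adjusts for exposure, not for detection. The tiers grade certainty without equalising the chance of being diagnosed.

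**The case against.** The strongest reply is that the EHR variable is only part of the endpoint. Caregivers in both arms are surveyed at 12 and 24 months, outside the CDS prompts, and both arms are followed through sick, allergy and ED visits to 30 months, so later presentation may narrow an early gap. This stands as mitigation. But the surveys cover consenting caregivers only, linkage to the EHR needs permission (section 8.1), and caregiver report is the lowest tier.

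Three stronger readings are tempting, and the documents support none of them.

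- A reader might infer that never-exposed, never-tested infants are counted as allergy-free. The yes/no variable and the absence of an undetermined category suggest it, but no passage says so. The algorithm is in the MOP, which is not among these documents, and such infants might be treated as missing. Any such rule would also apply to both arms.
- A reader might infer that the bias runs against the intervention throughout. Guided testing and referral concern high-risk infants. For low-risk infants, section 5.5 lists fewer unnecessary allergist referrals as a possible benefit, which could lower detection in the intervention arm.
- A reader might infer that the CDS fields feed the endpoint. They are extracted, but no passage gives them that use. Dropping them would also leave any extra diagnoses that prompting produces in ordinary fields.

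It is also fair to say that exposure and testing data are already collected (Table 8.1, Table 8.2) and that section 13.4.6 reports reactions. What is missing is a comparison of exposure and testing by arm and an analysis of differential detection.

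**Conclusion.** The point holds in limited form. Prompting that can affect EHR detection exists in one arm by design, the documents do not state how never-exposed, never-tested infants are coded, and no planned analysis addresses arm-specific detection.

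If detection is higher in the intervention arm, most plausibly in high-risk infants, benefit would be masked or harm mimicked. In low-risk infants the direction is uncertain. The size cannot be derived from the documents. On assumed high-risk detection of 95% v 85%, power at the planned effect falls from about 80% to 64%, and the chance of a falsely significant harm rises from 2.5% to about 6%. These figures assume no false positives and make no allowance for what the surveys recover. The primary adherence endpoint is not affected by this point.

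**What to change.** Amend section 13.4.4, with matching text in the MOP.

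1. Define the yes/no endpoint only from sources available in the same form in both arms, and exclude intervention-only CDS fields. State how never-exposed, never-tested infants are coded.
2. Tabulate ever-exposed and ever-tested status by arm and risk stratum, showing the source of the information, because exposure is itself charted differently by arm.
3. Pre-specify two sensitivity analyses: one on the survey-based outcome, collected alike in both arms, and one arm-specific tipping-point analysis. The second varies detection in each arm and stratum, including equal and reversed values, and reports where the conclusion changes.

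Excluding never-exposed or never-tested infants is not a good substitute for item 3. It conditions on post-randomisation events that the intervention is meant to change, and control infants who eat peanut without a prompted note could be misclassified as never exposed.

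The cost is SAP and MOP wording and some extra analysis on data already collected. A few intervention-arm cases seen only in CDS fields would be lost. The survey-based analysis covers responders only, and its last survey is at 24 months rather than 30.
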